8.4 Reporting of Safety Events and Device Deficiencies/Complaints

The following events are to be reported to the Sponsor within 72 hours of the event occurrence and to the EC per their policy:

- All SAEs and USADEs
- All device issues that could possibly lead to an SAE

Additional follow-up information may be requested by the Sponsor. In addition, safety information may be shared with regulatory agencies and other participating sites, as required by applicable law and regulation.

If the event resulted in the death of a subject, the event shall also be reported via telephone to the Sponsor within 24 hours of knowledge of the event. SAEs will be reported to the local EC per their policy.

Sponsor contact for SAEs and UADEs:

[name], MD, PhD

[contact]

E-mail: [contact]

8.5 Device Deficiencies/Complaints

Device deficiencies/complaints should be reported to the study Sponsor contact identified on the cover page of this protocol. All device deficiencies/complaints will be collected, fully investigated, and documented in the source document and appropriate Sponsor document during the study reporting period. The PI is responsible for notifying the Sponsor in the event that there is any device issue that could potentially lead to a SAE.

9. ETHICAL CONDUCT OF THE STUDY

The study will be carried out in accordance with the protocol and with principles enunciated in the current version of the Declaration of Helsinki; the guidelines of Good Clinical Practice (GCP) for medical devices, as set forth by ISO 14155:2011 and ISO 14971:2012; applicable sections of U.S. FDA 21 Code of Federal Regulations (CFR); and applicable regulatory authority's requirements of the U.S.

The study will be conducted and reported in accordance with applicable policies of the EC and governing regulatory authorities.

9.1 Ethics Committee

The PI will ensure that approval from an appropriately constituted EC is attained for the clinical study prior to enrolling subjects, and PI will ensure that documentation of approval is maintained for the duration of the study.

The PI will ensure that the Sponsor is notified of any withdrawal of EC approval within 5 working days of such occurrence. If approval is terminated or suspended, the Principal Investigator will promptly notify the Sponsor and provide written explanation.

9.2 Regulatory Agencies and Competent Authority(ies)

The Sponsor will obtain approval from the local regulatory agency and competent authority (CA) before the start of the clinical trial, if necessary, per applicable local laws and regulations. Any additional requirements imposed by the EC or regulatory authority shall be followed, if applicable.

9.3 Management of Protocol Modifications and Amendments

Substantial amendments will only be implemented after approval of the EC.

A deviation is any instance(s) of failure to follow, intentionally or unintentionally, the requirements of the protocol. Under emergency circumstances, deviations from the protocol to protect the rights, safety, and wellbeing of human subjects may proceed without prior approval of the Sponsor and the EC/competent authority (CA). Such deviations shall be documented and reported to the Sponsor and the EC as soon as possible. Deviations will be reported as:

- **Critical Deviations:** Deviations that significantly affect the safety, efficacy, integrity, or conduct of the study. These deviations must be reported to the Sponsor no later than 5 working days from awareness of occurrence and reported to the EC per the deviation reporting policy.
- **Non-Critical Deviations:** Protocol deviations that do not significantly affect the safety, efficacy, integrity, or conduct of the trial. These deviations must be documented on the CRF Protocol Deviation page and will be reviewed by the study monitor.

Non-substantial modifications may be made during the normal course of device optimization, maintenance, and feasibility testing. Non-substantial modifications will be communicated to the CA as soon as possible, if applicable, and to the EC per their policy.

9.4 Participant Information and Informed Consent

The investigators will explain to each participant the nature of the study, its purpose, the procedures involved, the expected duration of exposure to the investigational product (if applicable), the potential risks and benefits, and any potential discomforts. Each participant will be informed that participation in the study is voluntary, that she may withdraw from the study at any time, and that withdrawal of consent will not affect her subsequent medical assistance and treatment. The participant must be informed that her medical records may be examined by authorized individuals other than their treating physician.

All participants for the study will be provided an ICF, describing the study and providing sufficient information to allow the participant to make an informed decision about her participation in the study. Informed consent documents will be subject to approval by the EC prior to enrolling subjects in the study.

The participant should read and consider the statement before signing and dating the ICF, and shall be given a copy of the signed document. The ICF must also be signed and dated by the PI (or his/her designee), and it shall be retained as part of the study records.

9.5 Early Termination of the Study

The Sponsor may terminate the study prematurely according to certain circumstances. Examples of such circumstances include ethical concerns, insufficient participant recruitment, participant safety concerns, alterations in

accepted clinical practice that make the continuation of a clinical trial unwise, early evidence of benefit or harm of the research product, or for any other reason.

10. STATISTICAL METHODS

10.1 Statistical Hypothesis

No statistical hypothesis is being tested in this study.

10.2 Sample Size Determination

The target sample size for this study is 30 subjects, providing 60 evaluable image sets for the image attribute review (30 PAC compression image sets and 30 TC compression image sets). The number of subjects was determined based on Sponsor discussions with a U.S. FDA Medical Officer, who indicated that, during MQSA re-accreditation, sites are requested to submit sample images. If an issue is identified with the sample images, an Advanced Mammographic Review occurs, where the quality of 30 images is assessed to determine whether the issue was isolated or systemic.

With a sample size of 30 image pairs, the 95% confidence interval width for the proportion of PAC image sets with equal or higher acceptability than TC image sets will be no wider than 13%, when the proportion is 95%.

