Procedures/Methods:	
The study population will consist of adult asymptomatic women presenting for screening 2D mammography. One breast of each subject will be identified as the “breast of interest,” which will undergo study-specific 3D imaging consisting of two-view (craniocaudal and mediolateral oblique) PA compression and image acquisition, followed by two-view technologist-controlled (TC) compression and image acquisition. The breast of interest will be randomly assigned to either the first breast imaged during the exam or the second breast imaged. TC compression and imaging, and procedures performed on the subject’s other breast will be conducted per standard of care.
 
Following image acquisition, 3D image quality evaluation will be conducted by MQSA-qualified readers. Prior to the reading session, images will be de-identified and the following information will be removed from the DICOM header to blind readers to the compression mode used during acquisition: time stamp, compression force, and breast thickness. The image sets will also be randomized for presentation during the image attribute reviews. Two (2) readers will evaluate each PAC and TC compression image set collected from each subject’s breast of interest and assess the acceptability of image attributes, as defined in the Guidance for Industry and FDA Staff - Class II Special Controls Guidance Document: Full-Field Digital Mammography System (2012). A third reader will provide adjudication, if there is disagreement for a given image set’s overall clinical image quality.
 
Workflow data, including the incidence of technologist intervention during acquisition and need for repeat image acquisition, will also be collected.
 
The proportion of PAC image sets that are of equal or higher acceptability than TC image sets will be calculated. A 95% confidence interval will be calculated using asymptotic method with continuity correction. The proportion of image sets indicated for repeated

	
image acquisition when using PA mode or TC mode will be summarized. Other endpoint data will be summarized using descriptive statistics. No statistical hypothesis is being tested in this study.

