4.2 Number Subjects

Up to 36 subjects will be enrolled into this study at one (1) site to achieve the targeted number of 30 complete and evaluable subjects.

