10.3.2 Analysis of Primary Endpoint

The proportion of PAC image sets that are of equal or higher acceptability than TC image sets will be calculated. A 95% confidence interval will be calculated using asymptotic method with continuity correction. This analysis will also be performed for subgroups defined by the randomized breast of interest (i.e. breast of interest imaged first versus breast of interest imaged second).

Proportion of images with acceptable overall image quality will be summarized for PAC image sets and TC image sets separately, with 95% confidence interval using asymptotic method with continuity correction.

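### The precision stated for 30 pairs (at most 13% wide at a proportion of 95%) is not what the prescribed interval gives: 14.5% truncated at 100%, 18.9% untruncated

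*Combined protocol and SAP*

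**What the plan says.** Section 10.2 (Sample Size Determination) takes the number 30 from the sponsor's discussion with a regulator's medical officer about a review based on 30 images. It then adds a precision statement. It opens with "With a sample size of 30 image pairs" and says that the interval for the proportion of PAC sets with equal or higher "acceptability than TC image sets will be no wider than 13%, when the proportion is 95"%. That section names no interval method and does not mention truncation.

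The method is fixed elsewhere. For the same proportion, section 10.3.2 (Analysis of Primary Endpoint) says: "A 95% confidence interval will be calculated using asymptotic method with continuity correction". The synopsis, under Procedures/Methods, repeats the instruction.

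Two other places bear on the point. Section 10.1 states that no hypothesis is tested. Section 4.2 allows for replacements: "Up to 36 subjects will be enrolled into this study at one (1) site", with 30 complete and evaluable subjects as the target.

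**The concern.** The sample size section and the analysis section describe the same interval for the same proportion, yet the width promised in the first does not come out of the method prescribed in the second. A continuity correction always widens the interval, and at n = 30 it adds 1/60, or 1.7 percentage points, on each side. A figure worked out without it is therefore too small.

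The plan has no hypothesis test, and so no power calculation. The 13% sentence is the only place where it says in numbers what 30 subjects will deliver for the primary endpoint. The results are meant to support regulatory submissions, and anyone who repeats this short calculation will see that the two sections do not agree. The discrepancy makes the study look more precise than its own method allows.

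**Working it through.** **Inputs**

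- n = 30 pairs (section 10.2).
- p = 0.95 (section 10.2).
- Confidence level 95% (sections 10.2 and 10.3.2). I take the interval as two-sided, because a width is quoted; z = 1.960. The documents do not state the sidedness.
- Method: asymptotic with continuity correction (section 10.3.2 and synopsis). I take this as the Wald interval with correction 1/(2n): p ± [z·√(p(1−p)/n) + 1/(2n)].
- Stated width: at most 13% (section 10.2).

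**1. The plan's own figure**

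Standard error = √(0.95 × 0.05 / 30) = 0.0398, and 1.96 × 0.0398 = 0.0780.

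Without continuity correction the limits are 0.95 ± 0.0780, that is 0.8720 to 1.0280. The width is 15.6% untruncated, or 1 − 0.8720 = 12.8% with the upper limit cut at 100%. The second value matches the stated 13%. That this is how the 13% arose is an inference.

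**2. The prescribed interval**

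Correction = 1/(2 × 30) = 0.0167. Half-width = 0.0780 + 0.0167 = 0.0947.

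Limits: 0.95 − 0.0947 = 0.8553 and 0.95 + 0.0947 = 1.0447.

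- Untruncated width: 2 × 0.0947 = 18.9%, which is 5.9 points above 13%.
- Truncated width: 1 − 0.8553 = 14.5%, which is 1.5 points above 13%.

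**3. Does a larger n rescue the sentence?**

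At the enrolment ceiling of 36, the half-width is 0.0712 + 0.0139 = 0.0851 and the limits are 0.8649 to 1.0351. The width is 13.5% truncated and 17.0% untruncated. With the prescribed method, 13% at p = 0.95 is first reached at 41 pairs (truncated) or 58 pairs (untruncated).

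**4. Does another 95% method rescue it?**

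Widths at n = 30, p = 0.95, each before any truncation:

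| Method | Width |
|---|---|
| Wilson | 17.9% |
| Wilson with correction | 20.7% |
| Clopper-Pearson | 19.4% |
| Agresti-Coull | 20.3% |

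Of the 95% intervals tried, only the uncorrected Wald interval with truncation comes in at or below 13%.

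**5. Results that can occur**

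Exactly 95% of 30 is 28.5, so the observed proportion cannot be 95%. The prescribed interval at the attainable results around it is:

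| Result | Limits (truncated) | Width, truncated | Width, untruncated |
|---|---|---|---|
| 28/30 (93.3%) | 82.7% to 100% | 17.3% | 21.2% |
| 29/30 (96.7%) | 88.6% to 100% | 11.4% | 16.2% |
| 30/30 (100%) | 98.3% to 100% | 1.7% | 3.3% |

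**The case against.** The arithmetic is not in dispute. The best defence concerns how the sentence should be read.

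First, 95% cannot be observed with 30 pairs. If the sentence is taken as a bound for results at or above 95%, the attainable ones are 29/30 and 30/30, and with truncation both meet it (11.4% and 1.7%). That is correct as far as it goes. But the sentence does not say at least 95%, the reading fails at 29/30 without truncation (16.2%), and the attainable result just below, 28/30, gives 17.3% even with truncation.

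Second, 95% might be meant as the assumed true proportion. Under a binomial distribution with n = 30 and p = 0.95, the truncated prescribed width has a mean of 13.2% and a median of 11.4%, and 29 or 30 favourable pairs occur with probability about 55%. On that reading 13% is roughly right. But the sentence sets a maximum, not an average, and the mean is itself slightly over 13%.

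Third, 18.9% includes 4.5 points above 100%, which no proportion can reach, so the like-for-like gap is 1.5 points. This is fair, and 14.5% is the figure to compare first. Both belong in the record because the plan does not say whether limits are truncated.

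Fourth, nothing hangs on the 13%: there is no margin, success criterion or decision rule tied to it, and 30 was not derived from it. This stands and limits the weight of the point. It does not make the sentence correct.

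**Conclusion.** The concern holds. For 30 pairs and a proportion of 95%, the interval that the plan prescribes is wider than the maximum that the plan states: 14.5% against 13% on the reading most favourable to the plan, and 18.9% if limits are not truncated.

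The conclusion rests on a two-sided 95% interval and on the usual 1/(2n) form of the continuity correction. It does not depend on how the 13% was obtained.

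The error lies in the precision statement alone. It does not undermine the choice of 30 subjects, and the interval finally reported will follow section 10.3.2 in any case. It should be corrected because it is the only quantitative statement of precision in the plan and it overstates what the study will deliver.

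**What to change.** Keep n = 30 and replace the precision sentence in section 10.2 with one that names the prescribed interval and says how limits beyond 100% are handled. For example:

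> With 30 image pairs, the 95% confidence interval (asymptotic with continuity correction, limits truncated at 100%) is 85.5% to 100% when the proportion is 95%, a width of about 14.5% (18.9% untruncated). It is 82.7% to 100% at 28/30 and 88.6% to 100% at 29/30.

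A shorter version that names the method, the truncation rule and the single width of 14.5% would also remove the contradiction. The two attainable results are worth including because 95% itself cannot be observed.

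If the sponsor would rather use a different interval, it should be changed in sections 10.2 and 10.3.2 and in the synopsis together, and the width recomputed for it.

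The recommended change costs one sentence. It needs no additional subjects and does not alter the analysis. The only drawback is a less favourable stated precision.

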10.3 Statistical Analysis

10.3.1 General Statistical Methods

The study data will be summarized using descriptive statistics. The descriptive statistics for continuous variables will include mean, standard deviation, median, Q1 and Q3, minimum, maximum, and sample size, as appropriate. Categorical variables will be described with counts, percentages, and sample size, as appropriate. A 95% confidence interval may be presented, when necessary.

10.3.2 Analysis of Primary Endpoint

The proportion of PAC image sets that are of equal or higher acceptability than TC image sets will be calculated. A 95% confidence interval will be calculated using asymptotic method with continuity correction. This analysis will also be performed for subgroups defined by the randomized breast of interest (i.e. breast of interest imaged first versus breast of interest imaged second).

Proportion of images with acceptable overall image quality will be summarized for PAC image sets and TC image sets separately, with 95% confidence interval using asymptotic method with continuity correction.

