4.6 Breast of Interest Randomization

One (1) breast per subject will undergo study-specific procedures (hereafter referred to as “breast of interest”) while the second breast will be imaged per standard of care. The breast of interest will be randomized across all subjects so that approximately half the subjects will be assigned to the first imaged breast and the other half will be assigned to the second imaged breast (Figure 2).

Site technologists conducting the study will perform each subject’s mammography exam per standard practice. Thus, the laterality of the breast of interest will solely depend on which breast (left or right) the technologist images first and second in standard practice.

[figure not shown]

Figure 2 – Schematic showing image acquisitions based on the randomly-assigned breast of interest (i.e. first or second breast).

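### The continuity-corrected asymptotic interval fails near 100% with 30 pairs (about 15 per subgroup): true coverage is 78.5% overall and 53.6% per subgroup at the plan's own 95%

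*Combined protocol and SAP*

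**What the plan says.** Section 10.3.2 specifies the interval for the primary proportion: "A 95% confidence interval will be calculated using asymptotic method with continuity correction". It extends this to the breast imaged first and the breast imaged second: "This analysis will also be performed for subgroups defined by the randomized breast of interest". It then asks for the proportion with acceptable overall quality in each compression mode, "with 95% confidence interval using asymptotic method with continuity correction". The synopsis repeats the method for the primary proportion.

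Section 10.2 sets the size: "The target sample size for this study is 30 subjects, providing 60 evaluable image sets for the image attribute review", that is, 30 pairs. It states that the interval width "will be no wider than 13%, when the proportion is 95" per cent. Section 4.6 says that "approximately half the subjects will be assigned to the first imaged breast and the other half will be assigned to the second imaged breast", which gives about 15 subjects per subgroup.

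Section 10.1 states: "No statistical hypothesis is being tested in this study". No exact or score interval is named anywhere as an alternative or as a fallback for proportions close to 100%.

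**The concern.** The usual asymptotic interval for a proportion takes its width from the estimated standard error, which shrinks to zero as the observed proportion approaches 100%. With 30 pairs and a true proportion near 95%, the expected number of failures is 30 × 0.05 = 1.5, too few for the normal approximation. With no failures, the data-driven part of the interval vanishes and a fixed correction of 1/(2n) is all that is left.

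The primary analysis has no test and no margin, so this interval is all that tells a reader how far the result can be trusted. Sections 1.1, 2.1 and 3.1 say the results are to support regulatory submissions. After 30/30, the report would appear to exclude a PAC-inferior rate above 1.7%, when 30 subjects exclude only rates above about 11.6%. The error favours the device, and it is largest in the best-looking result.

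**Working it through.** **Inputs.** n = 30 pairs and a planning proportion of 95% (section 10.2); about 15 per subgroup (section 4.6, half of 30); a 95% interval, asymptotic with continuity correction (section 10.3.2). Two-sidedness is not stated and is assumed, so z = 1.96.

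**Which interval is meant.** The text does not name it. The plan's own 13% width at n = 30 and p = 0.95 helps to identify it:

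| Interval | Width |
|---|---|
| Wald, no correction, cut at 100% (87.2% to 100%) | 12.8% |
| Wald, no correction, not cut | 15.6% |
| Wald with correction, cut at 100% (85.5% to 100%) | 14.5% |
| Wald with correction, not cut | 18.9% |
| Wilson | 17.9% |
| Wilson with correction | 20.7% |
| Clopper-Pearson | 19.3% |

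Only the first row meets the 13% limit: 1.96 × √(0.95 × 0.05/30) = 0.078, and 0.95 − 0.078 = 0.872. The planned interval is therefore read as Wald with the correction that section 10.3.2 adds:

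p̂ ± [1.96 × √(p̂(1 − p̂)/n) + 1/(2n)]

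The table also shows that the 13% omits the correction prescribed in 10.3.2.

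**Intervals at the likely results.** At 30/30 the square root is zero and 1/(2n) = 1/60 = 0.0167, so the lower limit is 0.983. The exact lower limit for n/n is 0.025^(1/n): 0.884 for n = 30 and 0.782 for n = 15.

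| Result | Planned formula | Clopper-Pearson |
|---|---|---|
| 30/30 | 98.3% to 101.7% | 88.4% to 100% |
| 29/30 | 88.6% to 104.8% | 82.8% to 99.9% |
| 28/30 | 82.7% to 103.9% | 77.9% to 99.2% |
| 15/15 | 96.7% to 103.3% | 78.2% to 100% |

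A single failure in 30 moves the planned lower limit from 98.3% to 88.6%.

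**Coverage.** Exact coverage at a true p is the sum of Binomial(n, p) probabilities over the results whose interval contains p.

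- n = 30, p = 0.95: the interval contains 0.95 for 24 to 29 successes. It misses at 30/30, with probability 0.95^30 = 0.2146, and at 23 or fewer, with probability 0.0006. Coverage = 1 − 0.2146 − 0.0006 = 78.5%.
- n = 15, p = 0.95: the interval contains 0.95 for 11 to 14 successes. Coverage = 1 − 0.95^15 − 0.0006 = 1 − 0.4633 − 0.0006 = 53.6%.

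| True p | n = 30 | n = 15 |
|---|---|---|
| 0.90 | 95.6% | 79.2% |
| 0.93 | 88.6% | 66.3% |
| 0.95 | 78.5% | 53.6% |
| 0.96 | 70.5% | 45.8% |
| 0.97 | 59.9% | about 100% |
| 0.98 | 45.4% | about 100% |

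Coverage bottoms out at about 40% just below p = 1 − 1/(2n), which is 0.983 for n = 30 and 0.967 for n = 15. Above that point it jumps to about 100%, because the perfect-score interval then contains p. Nearly all the shortfall comes from the perfect score, whose probability at n = 30 is 21.5% at p = 0.95 and 54.5% at p = 0.98.

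**Alternatives at n = 30.** At p = 0.95, Wilson covers 93.9% and Clopper-Pearson 98.4%. On a grid of 0.0001 over 0.95 to 0.98, Wilson ranges from 91.6% to 98.1%, and Clopper-Pearson never falls below 97.5%.

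**The case against.** The strongest reply is that section 10.3.2 never says Wald. A continuity-corrected Wilson interval is also asymptotic, covers 95.7% to 99.3% over 0.95 to 0.98 with 30 pairs, and gives 85.9% to 100% at 30/30. Under that reading the problem disappears. It is hard to reconcile with section 10.2, because that interval is 20.7% wide at 95%, not 13%. If it was intended, the plan must still name it and correct the width.

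Second, 95% is the only proportion in the documents, and it appears as an illustration of precision; 0.96 to 0.98 is an assumed range. The failure is also confined to a band: with 30 pairs, coverage is adequate at 0.90 and about 100% above 0.983. Both points stand, but coverage is already 78.5% and 53.6% at the plan's own value.

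Third, nothing is tested and no success criterion depends on the lower limit. The point estimate is unaffected, and a reader given the counts could compute an exact interval. That limits the harm to overstated precision. It does not justify printing as 95% an interval that does not reach it, in a study meant to support a submission. Upper limits above 100% are cosmetic and carry no weight here.

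**Conclusion.** The concern holds and should be fixed before analysis. With 30 pairs and a true proportion of 95%, the prescribed interval covers 78.5% instead of 95%; in a subgroup of 15 it covers 53.6%. Over the assumed range of 0.96 to 0.98 with 30 pairs, coverage falls from 70.5% to 45.4%, with a minimum of about 40% just below 0.983. A 30/30 result would carry a lower limit of 98.3% where the exact limit is 88.4%, and 15/15 would carry 96.7% where the exact limit is 78.2%. The separate PAC and TC proportions have the same weakness wherever the true rate lies in this band.

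The conclusion assumes a two-sided Wald interval with a 1/(2n) correction, 30 evaluable pairs and an even subgroup split. The consequence is overstated precision in the primary result, not a wrong test decision.

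**What to change.** In section 10.3.2, replace the asymptotic method with the two-sided 95% Clopper-Pearson interval for the primary proportion, both breast-order subgroups, and the separate PAC and TC proportions. Make the same change for the primary proportion in the synopsis. Wilson is an acceptable alternative, although its coverage falls to 91.6% at some values between 0.95 and 0.98.

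In section 10.2, restate the precision to match. At 95% with 30 pairs the Clopper-Pearson width is about 19% (Wilson about 18%), not 13%. Because 95% of 30 is not a whole number, it is clearer to give attainable results: 29/30 gives 82.8% to 99.9% (width 17.1 points) and 28/30 gives 77.9% to 99.2% (width 21.3 points).

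The cost is one phrase in two places and one restated figure. The interval is a standard software option and needs no change to design or sample size. Reported intervals will be wider at high proportions, which is what 30 subjects support. Making the change before data are seen avoids having to justify a later change of method in the final report under section 10.5.
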